10 SAFETY EVALUATION

10.1 Adverse Events

10.1.1 Definition

An adverse event or adverse experience (AE) is any untoward medical occurrence associated with the use of a drug in humans, whether or not considered drug related. Therefore, an AE can be ANY unfavorable and unintended sign (including an abnormal laboratory finding), symptom, or disease temporally associated with the use of a medicinal (investigational) product, whether or not considered related to the medicinal (investigational) product (attribution of ‘unrelated’, ‘unlikely’, ‘possible’, ‘probable’, or ‘definite’).

An AE is considered “unexpected” if it is not listed in the investigator brochure or is not listed at the specificity or severity that has been observed; or if an investigator brochure is not required or available, is not consistent with the risk information described in the general investigational plan in other study-related documents.

10.1.1.1 Diagnosis Versus Signs and Symptoms

If known, a diagnosis should be recorded on the CRF rather than individual signs and symptoms (e.g., record only liver failure or hepatitis rather than jaundice, asterixis, and elevated transaminases). However, if a constellation of signs and/or symptoms cannot be clinically characterized as a single diagnosis or syndrome at the time of reporting, each individual event should be recorded as an AE or SAE on the CRF. If a diagnosis is subsequently established, it should be reported as follow-up information.

10.1.1.2 Adverse Events Occurring Secondary to Other Events

In general, AEs occurring secondary to other events (e.g., cascade events or clinical sequelae) should be identified by their primary cause. For example, if severe diarrhea is known to have resulted in dehydration, it is sufficient to record only diarrhea as an AE or SAE on the CRF.

However, clinically significant AEs occurring secondary to an initiating event that are separated in time should be recorded as independent events on the CRF. For example, if a severe gastrointestinal hemorrhage leads to renal failure, both events should be recorded separately on the CRF.

10.1.1.3 Abnormal Laboratory Values

Only clinically significant laboratory abnormalities that require active management will be recorded as AEs or SAEs on the CRF (e.g., abnormalities that require study drug dose modification, discontinuation of study treatment, more frequent follow-up assessments, further diagnostic investigation, etc.).

If the clinically significant laboratory abnormality is a sign of a disease or syndrome (e.g., alkaline phosphatase and bilirubin 5 x the upper limit of normal associated with cholecystitis), only the diagnosis (e.g., cholecystitis) needs to be recorded on the Adverse Event CRF.

If the clinically significant laboratory abnormality is not a sign of a disease or syndrome, the abnormality itself should be recorded as an AE or SAE on the CRF. If the laboratory abnormality can be characterized by a precise clinical term, the clinical term should be recorded as the AE or SAE. For example, an elevated blood potassium level of 7 mEq/L should be recorded as “hyperkalemia”

Observations of the same clinically significant laboratory abnormality from visit to visit should not be repeatedly recorded as AEs or SAEs on the CRF, unless their severity, seriousness, or etiology changes.

10.1.1.4 Preexisting Medical Conditions (Baseline Conditions)

A preexisting medical condition should be recorded as an AE or SAE only if the frequency, severity, or character of the condition worsens during the study. When recording such events on an Adverse Event CRF, it is important to convey the concept that the preexisting condition has changed by including applicable descriptors (e.g., “more frequent headaches”).

10.1.2 Assessment of Severity

Assessment of severity is one of the responsibilities of the investigator in the evaluation of AEs and SAEs. Severity will be graded according to the NCI CTCAE v4.03. The determination of severity for all other events not listed in the CTCAE should be made by the investigator based upon medical judgment and the severity categories of Grade 1 to 5 as defined below.

Grade 1 (mild):

- An event that is usually transient and may require only minimal treatment or therapeutic intervention. The event does not generally interfere with usual activities of daily living.

Grade 2 (moderate):

- An event that is usually alleviated with additional specific therapeutic intervention. The event interferes with usual activities of daily living, causing discomfort but poses no significant or permanent risk of harm to the subject.

Grade 3 (severe)

- An event that requires intensive therapeutic intervention. The event interrupts usual activities of daily living, or significantly affects the clinical status of the subject.

Grade 4 (life threatening)

- An event, and/or its immediate sequelae, that is associated with an imminent risk of death or with physical or mental disabilities that affect or limit the ability of the subject to perform activities of daily living (eating, ambulation, toileting, etc.).

Grade 5 (fatal):

- Death (loss of life) as a result of an event.

It is important to distinguish between serious criteria and severity of an AE. Severity is a measure of intensity whereas seriousness is defined by the criteria in Section 10.1.2. A Grade 3 AE need not necessarily be considered an SAE. For example, a Grade 3 headache that persists for several

hours may not meet the regulatory definition of an SAE and would be considered a nonserious event, whereas a Grade 2 seizure resulting in a hospital admission would be considered an SAE.

10.1.3 Grading and Relationship to Drug

The descriptions and grading scales found in the CTEP Version 4 of the NCI Common Terminology Criteria for Adverse Events (CTCAE) will be utilized for AE reporting. CTEP Version 4 of the CTCAE is identified and located at:

http://ctep.cancer.gov/protocolDevelopment/electronic_applications/ctc.htm.

AEs not covered by specific terminology listed should be reported with common medical terminology, and documented according to the grading scales provided in the CTCAE Version 4.

The relationship of event to study drug will be documented by the Investigator as follows:

- **Unrelated:** The event is clearly related to other factors such as the participant's clinical state, other therapeutic interventions or concomitant drugs administered to the participant.
- **Unlikely:** The event is doubtfully related to investigational agent(s). The event was most likely related to other factors such as the participant's clinical state, other therapeutic interventions, or concomitant drugs.
- **Possible:** The event follows a reasonable temporal sequence from the time of drug administration, but could have been produced by other factors such as the participant's clinical state, other therapeutic interventions or concomitant drugs.
- **Probable:** The event follows a reasonable temporal sequence from the time of drug administration, and follows a known response pattern to the study drug. The event cannot be reasonably explained by other factors such as the participant's clinical state, therapeutic interventions or concomitant drugs.
- **Definite:** The event follows a reasonable temporal sequence from the time of drug administration, follows a known response pattern to the study drug, cannot be reasonably explained by other factors such as the participant's condition, therapeutic interventions or concomitant drugs; AND occurs immediately following study drug administration, improves upon stopping the drug, or reappears on re-exposure.

N.B.: When making the assessment on causality, it should be taken into consideration that immune-therapeutic agents have the potential to cause very late and/or permanent effects on the immune system, i.e., a causal relationship could exist despite a lack of apparent temporal relationship. Information provided in the IB and/or in "Background" of this protocol may support these evaluations.

10.1.4 Reporting Adverse Events**Table 11 Guidelines for Routine Adverse Event Reporting for Phase 1 Studies (Regardless of Expectedness)**

Attribution	Grade 1	Grade 2	Grade 3	Grade 4
Unrelated	X	X	X	X
Unlikely	X	X	X	X
Possible	X	X	X	X
Probable	X	X	X	X
Definite	X	X	X	X

Table 12 Guidelines for Routine Adverse Event Reporting for Phase 2 Studies (Regardless of Expectedness)

Attribution	Grade 1	Grade 2	Grade 3	Grade 4
Unrelated			X	X
Unlikely			X	X
Possible	X	X	X	X
Probable	X	X	X	X
Definite	X	X	X	X

Routine AEs occurring between the start date of intervention until 90 days after the last intervention, or until the event has resolved, the study participant is lost to follow-up, the start of a new treatment, or until the study investigator assesses the event(s) as stable or irreversible, will be reported. New information will be reported after it is received.

During the course of the study all AEs and SAEs should be proactively followed up for each subject. Every effort should be made to obtain a resolution for all events, even if the events continue after discontinuation/study completion.

If a subject discontinues from treatment for reasons other than disease progression, and therefore continues to have tumor assessments, drug or procedure-related SAEs must be captured until the patient is considered to have confirmed PD and will have no further tumor assessments.

The investigator is responsible for following all SAEs until resolution, until the subject returns to baseline status, or until the condition has stabilized with the expectation that it will remain chronic, even if this extends beyond study participation.

Follow-up of unresolved adverse events

Any AEs that are unresolved at the subject's last visit in the study are followed up by the investigator for as long as medically indicated, but without further recording in the eCRF. After 90 days, only subjects with ongoing investigational product-related SAEs will continue to be followed for safety.

AstraZeneca/MedImmune retains the right to request additional information for any subject with ongoing AE(s)/SAE(s) at the end of the study, if judged necessary.

Post study events

After the subject has been permanently withdrawn from the study, there is no obligation for the investigator to actively report information on new AE or SAEs occurring in former study subjects after the 90-day safety follow-up period for patients treated with durvalumab + tremelimumab+ olaparib. However, if an investigator learns of any SAEs, including death, at any time after the subject has been permanently withdrawn from study, and he/she considers there is a reasonable possibility that the event is related to study treatment, the investigator should notify the study sponsor and AstraZeneca/MedImmune Drug Safety.

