10.2.2 Olaparib Adverse Events of Special Interest (AESIs)

Adverse Events of Special Interest (AESIs) for olaparib are the Important Potential Risks of MDS/AML, new primary malignancy (other than MDS/AML) and pneumonitis.

ANY event of MDS/AML, new primary malignancy, or pneumonitis should be reported to AstraZeneca Patient Safety whether it is considered a non-serious AE [e.g. non-melanoma skin cancer] or SAE, and regardless of investigator's assessment of causality or knowledge of the treatment arm.

A questionnaire will be sent to any investigator reporting an AESI, as an aid to provide further detailed information on the event. During the study there may be other events identified as AESIs that require the use of a questionnaire to help characterize the event and gain a better understanding regarding the relationship between the event and study treatment.

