10.3.2 Reporting Serious Adverse Events

All new SAEs occurring from the date the participant signs the study consent until 90 days after the last intervention or a new treatment is started, whichever comes first, will be reported. The RPCI SAE Source Form is to be completed with all available information, including a brief narrative describing the SAE and any other relevant information.

SAEs that are unexpected and possibly, probably or definitely related must be reported as an Unanticipated Problem. Please refer to **Section 10.6** for details on reporting Unanticipated Problems.

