10.4 Investigator Reporting: Notifying the Study Sponsor

All SAEs will be reported, whether or not considered causally related to the investigational product, or to the study procedure(s). The reporting period for SAEs is the period immediately following the time that written informed consent is obtained through 90 days after the last dose of durvalumab + tremelimumab + olaparib or, until the initiation of alternative anticancer therapy.

The investigator and/or Sponsor are responsible for informing the Ethics Committee and/or the Regulatory Authority of the SAE as per local requirements.

The investigator and/or sponsor must inform the FDA, via a MedWatch form, of any serious or unexpected adverse events that occur in accordance with the reporting obligations of 21 CFR 312.32, and will concurrently forward all such reports to AstraZeneca. A copy of the MedWatch report must be faxed to AstraZeneca at the time the event is reported to the FDA. It is the responsibility of the sponsor to compile all necessary information and ensure that the FDA receives a report according to the FDA reporting requirement timelines and to ensure that these reports are also submitted to AstraZeneca at the same time.

* A *cover page* should accompany the **MedWatch** form indicating the following:

- “Notification from an Investigator Sponsored Study”
- The investigator IND number assigned by the FDA
- The investigator’s name and address
- The trial name/title and AstraZeneca ISS reference number (ESR-16-11751)

* Sponsor must also indicate, either in the SAE report or the cover page, the *causality* of events *in relation to all study medications* and if the SAE is *related to disease progression*, as determined by the principal investigator.

* *Send SAE report and accompanying cover page by way of email to AstraZeneca’s designated mailbox:*

[contact]

If a non-serious AE becomes serious, this and other relevant follow-up information must also be provided to AstraZeneca and the FDA.

Serious adverse events that do not require expedited reporting to the FDA still need to be reported to AstraZeneca preferably using the MedDRA coding language for serious adverse events. This information should be reported on a monthly basis and under no circumstance less frequently than quarterly.

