CTCAE Common Terminology Criteria for Adverse Events; IM Intramuscular; IV Intravenous; NCI National Cancer Institute.

Non-immune-mediated Reactions		
Severity Grade of the Event (NCI CTCAE version 4.03)	Dose Modifications	Toxicity Management
Any Grade	Note: Dose modifications are not required for AEs not deemed to be related to study treatment (i.e., events due to underlying disease) or for laboratory abnormalities not deemed to be clinically significant.	Treat accordingly, as per institutional standard.
Grade 1	No dose modifications.	Treat accordingly, as per institutional standard.
Grade 2	Hold study drug/study regimen until resolution to \leq Grade 1 or baseline.	Treat accordingly, as per institutional standard.
Grade 3	Hold study drug/study regimen until resolution to \leq Grade 1 or baseline. For AEs that downgrade to \leq Grade 2 within 7 days or resolve to \leq Grade 1 or baseline within 14 days, resume study drug/study regimen administration. Otherwise, discontinue study drug/study regimen.	Treat accordingly, as per institutional standard.
Grade 4	Discontinue study drug/study regimen (Note: For Grade 4 labs, decision to discontinue should be based on accompanying clinical signs/symptoms, the Investigator's clinical judgment, and consultation with the Sponsor.).	Treat accordingly, as per institutional standard.

Note: As applicable, for early phase studies, the following sentence may be added: "Any event greater than or equal to Grade 2, please discuss with Study Physician."

AE Adverse event; CTCAE Common Terminology Criteria for Adverse Events; NCI National Cancer Institute.

Appendix H Schedule of study procedures: Follow-up for subjects who have completed durvalumab, tremelimumab and olaparib treatment and achieved disease control (until confirmed progression of disease) and subjects who have discontinued study treatment due to toxicity in the absence of confirmed progression of disease

Evaluation	Time Since Last Dose of Durvalumab or Tremelimumab or Olaparib							
	Day (± 3)	Months (± 1 week)						12 Months and Every 6 Months (± 2 weeks)
	30	2	3	4	6	8	10	
Physical examination ^a	X							
Vital signs (temperature, respiratory rate, blood pressure, pulse) ^b	X							
Weight	X							
Urine hCG or serum β hCG	X							
AE/SAE assessment	X	X	X					
Concomitant medications	X	X	X					
Palliative radiotherapy	As clinically indicated 							
ECOG performance status	X	X	X		X (and month 9)			X
Subsequent anti-cancer therapy	X	X	X	X	X	X	X	X

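### Section 10.1.4 requires related SAEs to be captured until confirmed progression, but Appendix H schedules no AE/SAE assessment after month 3 and SAE reporting closes at 90 days

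*Combined protocol and SAP*

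**What the plan says.** Section 10.1.4 sets a rule for one group of patients: "If a subject discontinues from treatment for reasons other than disease progression, and therefore continues to have tumor assessments", then "drug or procedure-related SAEs must be captured until the patient is considered to have confirmed PD and will have no further tumor assessments". It gives no limit in days.

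The other texts on the same period are shorter:

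- Section 10.1.4, further down, under the follow-up of unresolved events: "After 90 days, only subjects with ongoing investigational product-related SAEs will continue to be followed for safety".
- Section 10.3.2, on new SAEs from consent onward: "until 90 days after the last intervention or a new treatment is started, whichever comes first, will be reported".
- Section 10.4, on the SAE reporting period: "through 90 days after the last dose of durvalumab + tremelimumab + olaparib or, until the initiation of alternative anticancer therapy".
- Section 10.7: deaths more than 90 days after the last dose count for the survival analysis but are not reported as SAEs.
- Section 12.5: refers to a safety follow-up of 30 days.
- Appendix H, which covers completers with disease control and patients who stopped for toxicity without confirmed progression: the row "AE/SAE assessment" is marked at day 30, month 2 and month 3, and is blank afterwards. Scans continue every 12 weeks until confirmed progression. For toxicity discontinuations they may also end when standard therapy or another study begins.

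**The concern.** A mandatory duty with no day limit sits beside a schedule and two reporting windows that stop at about three months. A site working from Appendix H and the 90-day limits has no prompt to ask about new related SAEs after month 3, although Section 10.1.4 still requires them to be captured.

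What is at stake is the completeness of the late safety data. Section 10.1.3 itself warns that immune therapies can act very late, so that a causal link may exist without an obvious link in time. Section 6.2.1.2 also allows completers with disease control to be retreated after progression if they have no significant toxicity. If the rule extends to completers, an unrecorded late related SAE would also bear on that decision.

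**Working it through.** The plan gives no figure to reproduce, and no sample size, power or alpha enters. The check is a side-by-side reading and some calendar arithmetic.

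**1. Which texts govern these patients?** Section 6.8 sends patients permanently off study drug to both Section 10 and Appendix H (or Appendix I, after progression) for safety follow-up. Neither source is said to override the other, so a difference between them is a real conflict.

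**2. Are the blank cells in Appendix H genuine?** The table has eight columns: day 30; months 2, 3, 4, 6, 8 and 10; and month 12 with every 6 months after. The row for subsequent anti-cancer therapy is marked in all eight. The AE/SAE row is marked in the first three only. The columns survived text extraction, so the blanks look intended.

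**3. How much time is uncovered?** Inputs: a 90-day window, and a 12-month horizon chosen only for illustration.

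- Uncovered days in the first year off treatment: 365 − 90 = 275.
- Share: 275 / 365 = 75%.
- Beyond one year, the gap runs on for as long as the patient stays progression-free and is still scanned.

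**4. Which contacts fall in the gap?** After month 3, Appendix H has contacts at months 4, 6, 8, 9 (ECOG), 10 and 12. That is six contacts, and none carries an AE/SAE assessment.

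For scans in a patient who stops for toxicity: 275 / 84 = 3.3, so three or four 12-weekly scans fall in the uncovered part of the first year, depending on when treatment stopped.

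For a completer on the same schedule: the last durvalumab dose, on Cycle 13 Day 1, is at week 12 × 4 = 48, and olaparib ends at about week 52. Ninety days is 90 / 7 = 12.9 weeks, so the window closes at about week 52 + 12.9 = 65. Scans counted from first infusion fall at weeks 60, 72, 84 and 96. Three of these four come after the window closes.

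**5. Does other text close the gap?**

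- The post-study paragraph of Section 10.1.4 asks investigators to pass on related SAEs that they learn of, but only after permanent withdrawal from the study. Patients still being scanned under Appendix H have not been withdrawn.
- Section 10.2.2 says that "ANY event of MDS/AML, new primary malignancy, or pneumonitis should be reported to AstraZeneca Patient Safety" and sets no time limit. It covers three olaparib event types and schedules no assessment.

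Both are passive. Neither provides a scheduled question about related SAEs in general.

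**The case against.** The best defence is that the texts can be read together. Sections 10.3.2 and 10.4 set a 90-day window for SAEs of any cause, and Section 10.1.4 adds a longer rule for related SAEs in one subgroup. The 90-day sentence within 10.1.4 could be confined to events already open, since it stands under that subheading. A site could then comply by recording related SAEs at contacts it already makes. This has force: it shows that compliance is possible, and that it would go too far to say every site following the schedule must breach the rule. But no section states this reading, the 90-day limits carry no exception, and the schedule gives no prompt.

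The objection also holds against several stronger readings that a reader might infer:

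- **That these patients have no visits.** Scans, ECOG checks and therapy or survival contacts continue. What is missing is the AE/SAE assessment.
- **That the gap falls on the longest responders.** The rule is triggered when a subject discontinues. Section 8.1.5 and the title of Appendix H separate completers from discontinuations, so coverage of completers is an inference from the shared schedule.
- **That late MDS/AML would be lost.** Section 10.2.2 makes it reportable without a time limit. Section 1.3.2.4 gives 22 of 2618 (0.84%), which for 27 to 36 patients is 0.23 to 0.30 expected cases in all. It gives no onset times, so the share arising after day 90 cannot be estimated.
- **That this group is the most likely to have late events.** Nothing in the documents shows this.

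**Conclusion.** The contradiction is real and should be resolved. For patients who clearly fall under the rule, those who stop for toxicity without progression, Section 10.1.4 requires related SAEs to be captured until confirmed progression. The Appendix H row stops at month 3, and Sections 10.3.2 and 10.4 close at 90 days without exception. In the first year off treatment about 75% of the time, and all six later Appendix H contacts, lack a scheduled AE/SAE assessment.

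This supports saying that late related SAEs could be under-recorded. It does not support saying that the safety results would be understated: the number of such events cannot be derived from the documents, and investigators may record them unprompted. The 75% rests on the one-year horizon and on a patient who stays progression-free and starts no new therapy.

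The primary endpoints are not affected. DLTs are assessed over the first 8 weeks in a Phase I part already completed, and the Phase II test uses 3- and 6-month progression-free rates.

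**What to change.** State one window for drug- or procedure-related SAEs and use it throughout. To keep the existing Section 10.1.4 rule:

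- In Appendix H, extend the AE/SAE row to the contacts and scan visits already scheduled after month 3, until confirmed progression, limited to drug- or procedure-related SAEs.
- In Sections 10.3.2 and 10.4, and in the 90-day sentence of 10.1.4, name the 10.1.4 group as an exception.
- Bring Section 10.7 (deaths after 90 days) and the 30-day period in Section 12.5 into line.
- State in 10.1.4 whether patients who complete 12 months of treatment are covered.

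If the sponsor intends a shorter window, the 10.1.4 rule has to change instead. Either way the sections must agree. A separate check for the Section 10.2.2 events is not needed to resolve the conflict, because those are already reportable without a time limit.

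The cost is one schedule row, a few sentences and a few more SAE forms. No visit or test is added.
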